During the perimenopause, the incidence of depression increases ¹⁻⁵ and predicts increased all-cause and cardiovascular mortality ⁶. A role of estradiol withdrawal in the onset of mood disorders in some perimenopausal women has been suggested indirectly by estradiol's antidepressant efficacy and safety in perimenopausal depression ^{7:8}. Moreover, observational studies report the emergence of depressive symptoms after the discontinuation of menopausal hormone therapy (HT) in 5-10% of women ⁹⁻¹¹. The coincidence of declining ovarian function with the onset of depression led to the inference that "withdrawal" from physiologic estradiol levels underpinned depression during the perimenopause. To test this inference, we undertook a study to examine the role of estradiol withdrawal in perimenopausal depression. We evaluated the effects of the acute withdrawal of estradiol therapy in postmenopausal women with and those without a past perimenopausal depression. Results demonstrated that estradiol withdrawal induces depressive symptoms in women with a past perimenopausal depression, but not in those without such a history ¹². This study was the first to provide direct evidence that estradiol withdrawal is the relevant physiologic trigger for depressive symptoms in women with this condition. In women with past perimenopausal depression, the recurrence of depressive symptoms during blinded hormone withdrawal suggests that normal changes in ovarian estradiol secretion can trigger an abnormal behavioral state in these susceptible women. These data also suggest that the effects of estradiol withdrawal are processed differently in some women, presumably by altering the brain network composition or activity that underlies affective state. In this next protocol, we will examine a possible mechanism mediating the effects of estradiol-withdrawal on mood symptoms in asymptomatic postmenopausal women with a past

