Moreover, selective agonists of estrogen receptor beta have been demonstrated to attenuate the behavioral and HPA axis response to stress¹⁷⁻¹⁹. Results of this study will determine the role of ER beta in estradiol withdrawal-induced mood symptoms and, possibly, suggest the efficacy and safety of this compound as a treatment for depression during the perimenopause.

Given the markedly different adverse effect profiles of ER alpha and beta agonism, the results of this study may substantially impact current treatment recommendations for women with perimenopausal depression.

Justification for study sample: The sample of women who will be recruited for this protocol consists of women who have a history of a Structured Clinical Interview for DSM V (SCID) confirmed major or minor depression in the context of the perimenopause and who now are asymptomatic and postmenopausal. Our prior findings and those of others^{7,8} have demonstrated the short-term antidepressant effects of estradiol in this condition. Longitudinal studies also have demonstrated that the onset of depression in these women typically occurs during a stage of the perimenopause (stages of reproductive aging workshop [STRAW] stage -1) characterized by estradiol withdrawal. The results of our most recent study now provide, for the first time, direct evidence that estradiol withdrawal triggers a recurrence of depressive symptoms in these women (but not in matched controls). It is unclear whether the relevant signal in perimenopausal depression is mediated through estrogen receptor alpha or estrogen receptor beta. Consequently, we want to use the same design described above in euthymic women with a past history of perimenopausal depression to investigate whether the physiologically-relevant signal is mediated by estrogen receptor beta. Drawing our sample from this population ensures the inclusion of women who have been shown to be differentially sensitive to declining estradiol levels and who will likely develop

mood symptoms in our withdrawal paradigm, critical for demonstrating the role of ER beta in perimenopausal depression.

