The administration of 17 β -estradiol via a transdermal system was chosen for this study because it has several relevant advantages over oral preparations ^{37,38}. First, it delivers the primary ovarian estrogen, estradiol, into the circulation at a constant rate and results in sustained and easily measurable plasma levels of estradiol and in estrone/estradiol ratios less than one (as seen in the pre-climacteric period of life) ³⁹. Second, it delivers sufficient estradiol into the circulation to raise estradiol plasma concentrations to levels similar to those of women in the early follicular to mid-follicular phases of the menstrual cycle ^{37,40-42}, levels reported by some investigators as the minimum necessary for the relief of menopausal symptoms, particularly hot flushes ⁴⁰, without increasing synthesis of renin substrate. An increase in renin substrate has been suggested to accentuate or initiate the development of high blood pressure in susceptible women with other predisposing factors ⁴³ and has been implicated as a factor in the association of hypertension with the administration of oral conjugated estrogen ⁴⁴. In our experience with the transdermal estradiol patch in over 100 women in several protocols, it has been well tolerated, and, with the exception of an occasional skin rash, we have observed no adverse effects. With the application of the estrogen patch every three days, patient compliance has been reported to be excellent, and only occasional local irritation has been observed ⁴⁰.

Provera

Provera and synthetic progestins are widely prescribed, with indications including dysfunctional uterine bleeding, endometriosis, mastodynia, galactorrhea, and precocious puberty ⁴⁵.

Provera is widely prescribed to induce menses and shedding of the endometrial lining in women receiving ET. In our experience and that of others ⁴⁶, a daily dose of 5 mg for seven days is sufficient to successfully induce menses in women receiving 3-8 weeks of ET.

2. Study Objectives

a. Primary objectives

To determine whether the selective ER beta agonist LY500307 prevents mood symptoms (as measured by the CES-D and HRSD) from developing after the acute withdrawal of ET under double-blind, placebo-controlled conditions in asymptomatic postmenopausal women who have previously experienced a carefully confirmed perimenopause-related depression. Additionally, we will assess the safety of LY500307 in the context of this study.

b. Secondary objectives

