8. Pregnant women; sexually active women will be required to employ barrier contraceptive

methods;

9. Cerebrovascular disease (stroke);

10. Recurrent migraine headaches;

11. Women who have had a hysterectomy before one year after their last menstrual period;

12. NIMH employees/staff and their immediate family members will be excluded from the study per NIMH policy.

4. Study Design and Methods

a. Study overview

Participants will be screened over 3-4 clinic visits to ensure inclusion criteria is met.

Following screening, the medication phase of this study is a seven-week randomized, double blind, placebo controlled study and there is a four week follow-up evaluation phase to monitor all women for the emergence of adverse effects post-medication exposure. Participants will have weekly outpatient visits, weekly blood draws and will also complete daily symptom rating scales. The study involves a three week baseline phase in which all women receive open label (OL) estradiol therapy (ET) at a dose of 100 micrograms per day by transdermal skin patch, after which all women receive three weeks of double blind (DB) medication (i.e., LY500307 [at a daily dose of either 25 mg or 75 mg] or placebo), and then in non-menstruating women (i.e., the absence of reported menstrual bleeding of greater than 1-2 days during the double blind phase of this study), one week of Provera to precipitate a progestin-induced menses. The week of Provera is not a research-related intervention but is clinically-indicated to induce endometrial shedding that will eliminate potentially abnormal endometrial tissue consequent to the three weeks of unopposed estradiol exposure. The duration of the OL and DB phases of this study were selected to match those employed in our previous protocol (03-M-0175) ¹² in which we demonstrated that three weeks of estradiol followed by a three week withdrawal of estradiol were sufficient for the majority of

women (who met identical selection criteria as in this study) randomized to estrogen withdrawal to develop a recurrence of their mood symptoms after a three week asymptomatic period while on OL estradiol.

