All participants will be instructed to ingest study medications on an empty stomach after an overnight fast, since in all clinical pharmacology studies, LY500307 was administered orally after overnight fast, followed by breakfast approximately 30 minutes after the dosing. The effect of food on LY500307 has not been formally assessed. All participants will receive three capsules of LY500307 or placebo each morning consisting of the following formulations: 1) women randomized to 75 mg LY500307 will receive three capsules each containing 25 mg LY500307; 2) women randomized to 25 mg LY500307 will receive one capsule containing 25 mg LY500307 and two capsules of placebo; and 3) women randomized to placebo will receive three capsules each containing placebo. There will be a 1-1-1 distribution of women in each study arm (i.e., each arm will contain 15 women). A table of random numbers will be used for randomization in this trial. A set of numbers, equivalent to the proposed “N” will be selected and an appropriate block size within that set will be chosen. Within that block, the highest third of the numbers will be assigned to one treatment arm, the middle third will be assigned to the second treatment arm, and the lowest third will be assigned to a third treatment arm. The block size is not revealed to the investigator.

Genetics Studies: Subjects will be invited to provide a 30ml blood sample for genetic characterization studies, including investigation of specific gene polymorphisms (e.g., estrogen, progesterone and androgen receptors) and establishment of lymphoblastoid cell lines (LCLs) and induced pluripotent cell (IPCs) for epigenomic (WES), and transcriptomic (WTS) sequencing. We also plan to perform whole genomic sequencing (WGS) in this protocol in the future. The potential relevance of genetic polymorphisms for women with menstrual cycle-related mood disorders is evidenced in our recent studies (Dubey et. al, 2017; Rudzinskas et. al, 2020), where we have

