Access by other researchers to the study data is an important component of this study. Most commonly, researchers seek access to de-identified clinical data and biomaterials via the NIMH Center for Genetics (NCG), where data requests are handled by the Genomics Research Branch in the Office of the Director, NIMH, in accordance with a Distribution Agreement (<https://www.nimhgenetics.org/documents/Distribution%20Agreement.pdf>).

Access to clinical data and biomaterials not available through the NCG is handled by the PI, who works with the requestor and the NIMH Office of Technology Transfer to provide anonymized or coded data or biomaterials in accordance with an appropriate Material Transfer Agreement. Personally identifiable information is never shared outside the NIMH IRP.

d. Disposition

Samples and data will be kept indefinitely.

6. **Additional considerations**

a. Research with investigational drugs or devices:

LY500307 drug substance will be provided as active pharmaceutical ingredient (API) from Eli Lilly and Company allowing reference to the existing regulatory information in IND 100,916. The drug product will be prepared under a new IND for LY500307 (ER beta agonist) with the NIMH as the sponsor. [name] is the official representing the Institute.

Role of a commercial company: Eli Lilly will provide suitable amounts of active pharmaceutical ingredient (API) of LY500307 to the Contract Manufacturing Organization (CMO) where quality assurance tests will be performed and appropriately dosed capsules will be formulated.

In addition to drug substance, Eli Lilly and Company will provide the CMO with access to the information in the existing IND 100,916, including information on formulation development and drug product stability. The CMO we propose to employ is Pine Pharmaceuticals and is responsible for the manufacturing and release of the medications to be employed in this protocol. The facility at the Pine Pharmaceuticals, ([name]; website: www.PinePharmaceuticals.com, Ph [contact]) is an FDA certified facility for good manufacturing practice (c-GMP) and will produce the appropriate capsules containing LY500307 and matched placebos. Similar contracts are established with Pine Pharmaceuticals and the University of Iowa for the manufacturing and release of medications currently employed within other NIH protocols including several within the NIAID.

b. Gene therapy

Not applicable.

7. Risks and Discomforts

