b. Secondary outcome measures: the daily symptom rating form (DRF) consisting of a 14 item six point likert-type scale ⁴⁹ measuring the severity of several mood and behavior symptoms including hot flushes; the Beck Depression Inventory (BDI) ⁵⁰; and a visual analogue scale (VAS) measuring the reported severity of 13 mood and behavioral symptoms during the week prior to completion. Additionally, the relative impacts of LY500307 on ER alpha versus ER beta activity will be assessed by plasma LH, FSH, prolactin, and lipid levels, and endometrial thickness as measured by vaginal ultrasound. Finally, we plan to generate patient-derived LCLs and iPSCs from the women participating in this protocol to investigate both intrinsic cellular differences between women with PMD and controls as well as examining the effects of estradiol withdrawal with and without invitro exposures to an ER beta agonist.

10. Statistical Analysis

a. Analysis of data/study outcomes

The double blind will be broken and the randomization status of each participant will be revealed only after the completion of this study in all 45 women. Interim **blinded** analyses will be performed episodically (for example prior to the PI's Board of Scientific Counsellors) to inform ongoing scientific efforts and productivity of the Branch; however, these interim analyses will not serve as the basis for decisions to change study procedures or to terminate the study. Both study outcome measures and safety assessments will be reviewed by the DSMB.

We will first test for significant differences in mood symptoms arising during the double blind (DB) conditions compared with the open label (OL) ET (baseline) conditions in each of the three groups (i.e., women with past PMD randomized to DB LY500307 [25mg or 75mg] or placebo). Second, we will compare symptom ratings during DB treatment conditions across randomization groups (i.e., women with past PMD who were randomized to either DB LY500307 or placebo).

We will obtain six repeated measures on the same woman during two phases: baseline OL

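### Estradiol is stopped openly, so the within-arm tests listed first cannot show withdrawal symptoms or their prevention; the blinded LY500307-versus-placebo contrast should be the unconditional primary analysis

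*Combined protocol and SAP*

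**What the plan says.** All references are to the combined protocol and SAP.

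- **Objective.** Section 2a asks whether LY500307 prevents mood symptoms "from developing after the acute withdrawal of ET under double-blind, placebo-controlled conditions".
- **Baseline phase.** Section 4a: "all women receive open label (OL) estradiol therapy (ET) at a dose of 100 micrograms per day by transdermal skin patch", for three weeks.
- **Blinded phase.** Section 4a: "women randomized to placebo will receive three capsules each containing placebo". Section 6a says the manufacturer "will produce the appropriate capsules containing LY500307 and matched placebos". The schematic legend also lists placebo as oral, and the only patch in it is estradiol. Section 4d names three arms: 25 mg, 75 mg and placebo.
- **Earlier trial.** The Introduction describes a comparison with women kept on estradiol under double-blind conditions. Its justification of the study sample then says of the present trial: "we want to use the same design described above in euthymic women with a past history of perimenopausal depression".
- **Analysis.** Section 10a: "We will first test for significant differences in mood symptoms arising during the double blind (DB) conditions" against the open-label baseline, in each of the three groups. The comparison across randomised groups comes second. When Section 10a returns to that second analysis, the words *if necessary* stand before the inclusion of the OL mean as covariate. P values are Bonferroni-adjusted (k = 3 to 6), with two-sided 0.05.
- **Main comparison.** Sections 4d and 9a say the main comparisons are between LY500307 and placebo. Section 10b powers that difference.

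**The concern.** In the earlier trial, blinding covered the withdrawal itself, and the Précis relies on this: "the recurrence of depressive symptoms during blinded hormone withdrawal suggests" that normal hormone changes can trigger an abnormal mood state. Here a woman knows when her patch stops, and nothing in the text masks the switch from the HRSD rater.

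A within-arm rise from OL to DB therefore has several possible sources: loss of estradiol, knowing that estradiol has stopped, passage of time, starting capsules, and regression to the mean. The last arises because women are randomised only after the baseline ratings confirm that they have no clinically significant mood symptoms. No arm separates these sources.

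Two misreadings are at stake. A significant rise on placebo could be taken as estradiol-withdrawal symptoms. A significant rise on placebo beside a non-significant one on LY500307 could be taken as prevention. The second is a fallacy whatever the blinding, because a difference in significance is not a test of a difference.

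**Working it through.** The plan states no figure on this point, so the main check sets the passages side by side.

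**Step 1: what is blinded.**

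| Element | Where | What it shows |
|---|---|---|
| Estradiol | 4a, 4d | Open-label patch, three weeks, all women |
| Placebo | 4a, 6a, schematic legend | Oral capsules only |
| Arms | 4d | None continues estradiol |
| Consent statement | 7, Estradiol Replacement | Tells women that estradiol is used in the first three weeks |
| Earlier trial's control | 1, Introduction | Estradiol maintained under blind conditions |

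The blinded element is the content of the capsules. Stopping estradiol is open and common to all arms.

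**Step 2: what each planned analysis identifies.** Let W be the effect of losing estradiol, E the sum of the non-hormonal shifts listed above, and D the effect of LY500307 on ratings in the DB phase.

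- Placebo, OL to DB: W + E.
- LY500307, OL to DB: W + E + D.
- LY500307 minus placebo, DB phase: D.

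If randomisation and capsule blinding keep E the same across arms in expectation, it cancels in the third line only.

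**Step 3: illustration of the within-arm test.** Inputs from the documents: n = 15 per arm (Section 3a); two-sided 0.05 with Bonferroni k = 3 to 6 (Section 10a). Assumptions: W = 0 and D = 0; E is the same in every arm and equals δ SDs of the change score; arms are independent; the test is a paired t test. The documents give no value for δ, so a range is shown.

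Noncentrality is λ = δ√n, with 14 degrees of freedom. The probability of significance in one arm is p = P(T > c) + P(T < −c), where T is noncentral t with noncentrality λ. The critical value c is 2.145 at 0.05, 2.718 at 0.05/3 and 3.069 at 0.05/6. For δ = 0.5, λ = 0.5 × 3.873 = 1.936.

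| δ | p at 0.05 | p at 0.05/3 | p at 0.05/6 |
|---|---|---|---|
| 0.1 | 6.5% | 2.4% | 1.2% |
| 0.2 | 11.2% | 4.6% | 2.6% |
| 0.3 | 19.2% | 8.9% | 5.4% |
| 0.5 | 43.8% | 25.7% | 17.5% |

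**Step 4: the pattern that looks like prevention.** The probability that placebo is significant and at least one LY500307 arm is not is p(1 − p²). At δ = 0.5 and level 0.05 this is 0.438 × (1 − 0.192) = 0.354. At δ = 0.3 it is 18.5%, and at δ = 0.1 it is 6.5%. At 0.05/3 the three values are 24.0%, 8.9% and 2.3%. The drug does nothing in any of these cases.

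The planned analysis is a mixed model with six repeated measures, AR(1) covariance and Kenward-Roger degrees of freedom. It would give different figures, but it would not separate W from E.

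**The case against.** The strongest reply is that the plan already puts weight on the right contrast. Sections 4d and 9a call LY500307 versus placebo the main comparison, Section 10b powers it, and Section 10a already provides for adjustment by the OL mean. No sentence says that prevention will be concluded from within-arm significance. All of this stands. What remains is the order in Section 10a, the p values attached to the within-arm changes, and the *if necessary*, which may qualify only the covariate or the whole second analysis.

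A reader might infer that the protocol misdescribes its blinding. The documents do not support that. The Précis attaches the double-blind, placebo-controlled conditions to LY500307, Section 2a can be read the same way, and Sections 4a and 10a label the estradiol phase as open label. Likewise, the Introduction's statement about reusing the design is loose: Section 4a says that the phase durations were matched, and Section 4e speaks only of a similar design. These are points to clarify. The absence of an estradiol-continued arm is a design choice, and such an arm is not needed to compare LY500307 with placebo.

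The direction of expectancy is also open. Every woman starts capsules with a two-in-three chance of active drug, and hope of benefit could offset or reverse a rise. The schematic drawing is missing from the text available, so the absence of an inert patch is inferred from its legend and from the dosing and manufacturing text.

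**Conclusion.** The point holds with a limited scope. Estradiol withdrawal is open as described, so the within-arm OL-to-DB tests cannot attribute a rise to estradiol loss, and a significant/non-significant pattern across arms cannot establish prevention.

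Two stronger readings are tempting and should be resisted. First, the drug comparison is not compromised: LY500307 versus placebo is randomised and blinded for capsules, and open withdrawal is shared by all arms. What it cannot do alone is show that placebo-arm symptoms are hormonal; for that the trial leans on the earlier blinded study. Second, this is not type I error inflation: a rise caused by expectancy or regression is a real within-arm change, and the problem is its attribution.

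The size is illustrative. A common shift of 0.1 to 0.5 SD gives significance in one arm in 6.5% to 43.8% of trials at 0.05, 2.4% to 25.7% at 0.05/3 and 1.2% to 17.5% at 0.05/6. At 0.1 to 0.2 SD the effect is small (6.5% to 11.2% at 0.05). The conclusion about attribution does not depend on these figures.

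**What to change.** 1. In Section 10a, name the between-arm contrasts of DB ratings (each dose versus placebo, adjusted for the OL mean) as the unconditional primary analysis and the sole basis for the prevention conclusion. Delete *if necessary*.
2. In Section 10a, report the within-arm OL-to-DB changes as estimates with confidence intervals, without significance claims and without attributing them to estradiol withdrawal.
3. In Section 2a and in the Introduction's justification of the study sample, state that estradiol withdrawal is open and that only LY500307 versus placebo is blinded. The Précis needs no change on this point.

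The cost is protocol wording and the order of two planned analyses, with no new participants or data. The sponsor gives up a within-arm significance claim.
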